- 5. Laboratory or clinical variables: X-rays, serological or microbiology tests for the conditions studied (HIV, HBV, HDC, Chagas disease, strongyloidiasis, and schistosomiasis). In addition, other laboratory parameters will be included (hemogram, including haemoglobin, platelets, leucocytes, neutrophils, lymphocytes, and eosinophils, IgE, liver and renal function creatinine, urea, AST, ALT, GGT, bilirubin, coagulation...)
- 6. Diagnostic variables: Diagnoses of each disease/condition (HIV, HBV, HCV, Chagas disease, strongyloidiasis, schistosomiasis and female genital mutilation) based in ICD 10 codes registered by health professionals in the last 10 years including the intervention period.
- 7. Drug related to the diseases included in the study (e.g., ivermectine for strongyloidiasis) prescribed during the intervention period.
- 8. Co-morbidities: Other diseases diagnoses based on ICD-10 codes registered by health professionals into the system in the last 10 years including the intervention period. The aim is to study the possible association of other diseases (diseases associated with immunosuppression, mental health conditions, cardiovascular and other diseases, other infectious diseases...) with the studied diseases/conditions. In addition, to carry out the cost-effectiveness study (an economic analysis that will be essential to achieve the second objective of the study) all parameters must be considered to adjust the model, including the comorbidities of the diseases.
- 9. Immunosuppression status: Here it will include the prescription and billing of immunosuppressive drugs in the last 10 years including the intervention period as well as ICD-codes on transplant, haematological diseases, cancer and related diagnoses, and autoimmune diseases in the last 10 years for determination of immunosuppression status.
- 10. Minimum basic data set (CMBD) variables: hospitalization dates, primary diagnoses during hospitalizations, laboratory parameters during hospitalizations, drugs prescribed during hospitalization or outpatient units, cost associated or attributed to hospitalization, number of visits in outpatient units

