- 7. Infección tuberculosa latente (ITL): Se decidió que no se implementará el cribado de ITL en Cataluña ya que nunca se ha realizado un cribado de forma sistemática para la ITL en Atención Primaria (AP), además de que la mayoría de los centros de AP no tienen acceso a la prueba diagnóstica IGRA, la prueba más coste-efectiva para detectar la ITL. Aunque no se creará una alerta específica para la ITL durante el proyecto, se recomienda que en un futuro se promueva la formación para poder implementar está infección en programas de cribado llevados a cabo en AP.
- **8. Estrongiloidiasis:** Se recomienda el cribado serológico de estrongiloidiasis a la población inmigrante procedente de países endémicos y si alguno de estos individuos está inmunosuprimido o tiene un potencial riesgo de ser inmunosuprimido en un futuro, se debería derivar a la unidad especializada del hospital de referencia y se debería realizar estudio de parásitos en heces.
- **9. Esquistosomiasis:** Se recomienda el cribado serológico de esquistosomiasis a la población inmigrante procedente de países endémicos.
- **10.** Enfermedad de Chagas: Se recomienda el cribado serológico de *T. cruzi* a la población inmigrante procedente de países endémicos.
- 11. Mutilación genital femenina (MGF): Se recomienda valorar el riesgo de MGF y detectar los casos en niñas y mujeres procedentes de países endémicos. Además, es necesario formar a los profesionales de la salud en competencia intercultural y en cómo abordar la temática en la consulta respetando la cultura de la mujer y de su familia.
- **12. Derivación:** Personas diagnosticadas de alguna de las patologías incluidas en el programa de cribado deben ser derivadas a la unidad especializada del hospital de referencia.

Annex 2. Screening recommendations for infectious diseases and FGM targeting the migrant population residing in Andalusia, Spain.

- 1. Población diana: Se ha definido como población diana del estudio a inmigrantes que procedan de países en África, Latino América, Asia y Europa del Este. Se utilizó la división geográfica de la Comisión de Estadística de las Naciones Unidas.
- 2. Virus de la inmunodeficiencia humana (VIH): Se recomienda el cribado universal de VIH a todos los inmigrantes procedentes de un país incluido en la definición de población diana si no se ha hecho una prueba de VIH con anterioridad. Repetir prueba de VIH si la persona es diagnosticada con otra ITS y/o presenta otros factores de riesgo.

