2.2 Specific Study Objectives

Primary objective 1: To compare the detection rate per month of all aggregated infections (HIV, HBV, HCV, TB, *T.cruzi*, *S.stercoralis* and *Schistosma spp.* infections) between the intervention and control centres over at least five years until the end of the intervention. In the Andalusian site, syphilis, latent TB and intestinal parasites will also be included.

Secondary objective 2: To compare the detection rate per month of each individual condition, the infections and FGM cases, between the intervention and control centres over at least five years until the end of the intervention.

Secondary objective 3: To compare the number of early HIV diagnoses between the intervention and control centres over at least five years until the end of the intervention.

Secondary objective 4: To compare the number of early HBV and HCV diagnoses between the intervention and control centres over at least five years until the end of the intervention.

Secondary objective 5: To compare the number of screening tests performed for all aggregated infections between the intervention and control centres over at least five years until the end of the intervention.

Secondary objective 6: To compare the number of screening tests performed for each individual condition between the intervention and control centres over at least five years until the end of the intervention.

Secondary objective 7: To estimate associations between the screening performance of all aggregated infections with different socio-demographic and epidemiological factors.

Secondary objective 8: To estimate associations between the screening performance of each individual condition with different socio-demographic and epidemiological factors.

Secondary objective 9: To measure the number of the diagnosed individuals with follow-up visits in the hospital of reference.

Secondary objective 10: To measure the number of the diagnosed individuals that have received treatment.

Secondary objective 11: To estimate the prevalence of each infection and FGM in the migrant population.

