Endpoint 6: The number of the screening tests performed for each individual condition will be compared between the intervention and control PCCs before and after the implementation.

Endpoint 7: Associations between the screening performance of the aggregated infections with different socio-demographic and epidemiological factors, such as, sex, age, geographic areas immunosuppression status, being attended in an intervention centre, fulfilling the screening criteria, among others, will be analysed.

Endpoint 8: Associations between the screening performance of each individual condition with different socio-demographic and epidemiological factors, such as, sex, age, geographic areas immunosuppression status, being attended in an intervention centre, fulfilling the screening criteria, among others, will be analysed.

Exploratory Endpoints

Endpoint 9: The number of migrant patients under follow-up in the hospital after a diagnosis of an infection or FGM will be estimated using the Minimum basic dataset (MBDS).

Endpoint 10: The number of migrant patients under treatment after a diagnosis will be estimated using the data from the EPR systems and MBDS.

Endpoint 11: The prevalence of each condition will be estimated using as the denominator the total number of tested migrant patients for that specific condition.

3. Study Methods

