| Migrants tested for active TB | N (%) |
| Migrants tested for latent TB [^] | N (%) |
| Migrants tested for a T.cruzi infection | N (%) |
| Migrants tested for a S. stercoralis infection | N (%) |
| Migrants tested for a Schistosoma spp. infection | N (%) |
| Migrants tested for intestinal parasites^ | N (%) |
| Migrants screened for FGM | N (%) |
| Migrants diagnosed with HIV | N (%) |
| CD4 cell count | Mean (SD) or Median (IQR) |
| HIV viral load | Mean (SD) or Median (IQR) |
| Migrants diagnosed with syphilis^ | N (%) |

| Migrants diagnosed with HBV | N (%) |
|--|---------------------------|
| Migrants diagnosed with HCV | N (%) |
| Migrants diagnosed with active TB | N (%) |
| Migrants diagnosed with latent TB [^] | N (%) |
| Migrants diagnosed with T.cruzi infection | N (%) |
| Migrants diagnosed with S.stercoralis infection | N (%) |
| Migrants diagnosed with Schistosoma spp. infection | N (%) |
| Migrants diagnosed with intestinal parasites^ | N (%) |
| Laboratory parameters | Mean (SD) or Median (IQR) |
| Migrants diagnosed with FGM | N (%) |
| Referrals to specialists | N (%) |
| Other diagnoses | N (%) |
| Comorbidities | N (%) |
| Drugs prescribed during the intervention | N (%) |
| Medication adherence (in days) | Mean (SD) or Median (IQR) |
| Hospitalised patients | N (%) |
| Diagnoses during hospitalisation | N (%) |
| Time hospitalised | Mean (SD) or Median (IQR) |
| Patients who needed Intensive Care Unit | N (%) |
| Drugs prescribed during hospitalisation | N (%) |
| Medication adherence of drugs prescribed during | Mean (SD) or Median (IQR) |
| hospitalisation (in days) | |
| Follow-up visits after hospitalisation | Mean (SD) or Median (IQR) |
| Diagnoses made during follow-up visits after hospitalisation | N (%) |
| Drugs prescribed during follow-up visits after hospitalisation | N (%) |
| Medication adherence of drugs prescribed in follow-up | Mean (SD) or Median (IQR) |
| visits after hospitalisation (in days) | |
| Cured patients | N (%) |
| Patients who died during the intervention period | N (%) |

HIV: human immunodeficiency virus, HBV: hepatitis B virus, HCV: hepatitis C virus, TB: tuberculosis, FGM: female genital mutilation, SD: standard deviation, IQR: interquartile range; N = frequency

Table 3. Associations of different factors with XX tests performed

| Variables | XX test performed n/N (%) | OR (95% CI) | p. value | aOR (95% CI) | p. value |

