| immune_drugs | Immunosuppressive drugs prescribed during the intervention period | Qualitative | ACT codes |
| doses | Prescribed drug doses | Quantitative | |
| tto_start | Treatment start date | Quantitative | MM/DD/YYYY: Up to 12/31/2024 |
| tto_end | Treatment end date | Quantitative | MM/DD/YYYY: Up to 12/31/2024 |
| cost | Cost of the prescribed drugs | Quantitative | In euros (€) |
| Hospital (MBDS) | | | |
| hosp | Hospitalisation | Qualitative | Yes/No |
| hosp_dx | Primary diagnosis | Qualitative | ICD9 or ICD-10 |
| hosp_dxother | Other diagnosis | Qualitative | ICD9 or ICD-10 |
| hosp_dates | Hospitalisation dates | Quantitative | MM/DD/YYYY: Up to 12/31/2024 |
| hosp_hgb | Haemoglobin | Quantitative | |
| hosp_plt | Platelets | Quantitative | |
| hosp_wbc | Leucocytes | Quantitative | |
| hosp_neut | Neutrophils | Quantitative | |
| hosp_lym | Lymphocytes | Quantitative | |
| hosp_eos | Eosinophils | Quantitative | |
| hosp_crea | Creatinine | Quantitative | |

| hosp_urea | Urea | Quantitative | |
|-----------------------|--|--------------|---|
| hosp_ast | AST | Quantitative | |
| hosp_alt | ALT | Quantitative | |
| hosp_ggt | GGT | Quantitative | |
| hosp_bili | Bilirubin | Quantitative | |
| hosp_act | Coagulation | Quantitative | |
| hosp_sympt | Symptoms | Qualitative | Fever, diarrhoea, rash, fatigue, ulcers, among others |
| hosp_uci | Need for an Intensive Care Unit | Qualitative | Yes/No |
| hosp_vent | Need for mechanical ventilation | Qualitative | Yes/No |
| hosp_drugs | Drugs prescribed | Qualitative | ACT codes |
| hosp_doses | Drug doses | Quantitative | |
| hosp_tto_start | Treatment start date | Quantitative | MM/DD/YYYY: Up to 12/31/2024 |
| hosp_tto_end | Treatment end date | Quantitative | MM/DD/YYYY: Up to 12/31/2024 |
| hosp_drugs_cost | Cost of the drugs | Quantitative | In euros (€) |
| hosp_cost | Cost attributed to hospitalisation | Quantitative | In euros (€) |
| Hospital follow-up (I | MBDS) | | |
| followup | Number of follow-up visits after hospitalisation | Quantitative | |
| followup_dates | Dates of follow-up visits after hospitalisation | Quantitative | MM/DD/YYYY: Up to 12/31/2024 |
| followup_dx | Diagnosis made during the follow-up visits | Qualitative | ICD9 or ICD-10 |
| followup_hgb | Haemoglobin | Quantitative | |
| followup_plt | Platelets | Quantitative | |
| followup_wbc | Leucocytes | Quantitative | |
| followup_neut | Neutrophils | Quantitative | |

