| followup_lym | Lymphocytes | Quantitative | |
| followup_eos | Eosinophils | Quantitative | |
| followup_crea | Creatinine | Quantitative | |
| followup_urea | Urea | Quantitative | |

| followup_ast | AST | Quantitative | | |
|--------------------|--|--------------|------------------------------|--|
| followup_alt | ALT | Quantitative | | |
| followup_ggt | GGT | Quantitative | | |
| followup_bili | Bilirubin | Quantitative | | |
| followup_act | Coagulation | Quantitative | | |
| followup_drugs | Drugs prescribed during follow-up visits | Qualitative | ACT codes | |
| followup_doses | Drug doses | Quantitative | | |
| followup_tto_start | Treatment start date | Quantitative | MM/DD/YYYY: Up to 12/31/2024 | |
| followup_tto_end | Treatment end date | Quantitative | MM/DD/YYYY: Up to 12/31/2024 | |
| followup_cost | Cost of the drugs | Quantitative | In euros (€) | |
| Health events | | | | |
| cured | Cured patients | Qualitative | Yes/No | |
| mortality | Patients who died during the intervention period | Qualitative | Yes/No | |

PC: Primary care, PCT: Primary care team, EAP: Equipo de Atención Primaria, PCC: Primary care centre, CAP: Centro de Atención Primaria, HIV: human immunodeficiency virus, HBV: hepatitis B virus, HCV: hepatitis C virus, TB: tuberculosis, FGM: female genital mutilation, ACT: Anatomical Therapeutic Chemical, ICD-9: International Classification of Diseases Ninth Revision, ICD-10: International Classification of Diseases Tenth Revision, MBDS: Minimum basic dataset; ^Only in the Andalusian site

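### SAP Annex 1 counts hospital follow-up only after an admission, whereas Endpoint 9 counts it after a diagnosis; people referred and seen as outpatients are not captured

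*SAP*

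**What the plan says.** The aim is set by diagnosis. Objective 9 (SAP section 2.2) reads "To measure the number of the diagnosed individuals with follow-up visits in the hospital of reference". Endpoint 9 (SAP section 2.3) reads "The number of migrant patients under follow-up in the hospital after a diagnosis of an infection or FGM will be estimated", with the minimum basic dataset (MBDS) as its only source. The matching row of SAP Table 4 is also keyed to diagnosis. None of the three mentions an admission.

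The variables are set by admission. In the hospital follow-up block of SAP Annex 1, `followup` is "Number of follow-up visits after hospitalisation" and `followup_dates` is "Dates of follow-up visits after hospitalisation". SAP Table 2 applies the same limit to visits, to diagnoses and to drugs ("Drugs prescribed during follow-up visits after hospitalisation"), and Table 3 applies it to visits. Within Annex 1 itself the drug row is less explicit: it says only "Drugs prescribed during follow-up visits".

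The protocol is wider. Its hospital dataset item (section 7, study variables, item 10) includes "drugs prescribed during hospitalization or outpatient units, cost associated or attributed to hospitalization, number of visits in outpatient units". Its screening recommendations say that people diagnosed with a programme condition "deben ser derivadas a la unidad especializada del hospital de referencia", that is, they must be referred to the specialised unit of the reference hospital (Annex 1 item 12; Annex 2 item 13 says the same).

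**The concern.** The route described after a positive result is treatment or referral to specialist care (protocol sections 6 and 8, Annexes 1 and 2). Admission is not part of it. Someone found by serology in primary care can attend the specialised unit and complete follow-up without a hospital stay. Under the Annex 1 definitions that person has no follow-up visit.

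Objective 9 is the plan's measure of whether detected people reach hospital care. If its count depends on admission, a low figure cannot be told apart from a programme whose referrals succeeded without admissions. The people who are counted would be a selected group, those with a hospital stay.

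The definition also governs what is extracted. SAP sections 3.4 and 5.1 make Annex 1 the list of variables that is collected and passed to the biostatistician. A visit type missing from that list may not be in the file when Endpoint 9 is analysed.

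**Working it through.** The plan states no follow-up, treatment or admission rate, so there is no figure of its own to reproduce. The check is a comparison of texts, followed by a bound under stated assumptions.

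**Step 1. Trigger for counting**

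- Objective 9, Endpoint 9 and Table 4: a diagnosis.
- Annex 1 `followup` and `followup_dates`; Table 2 visits, diagnoses and drugs; Table 3 visits: a prior hospitalisation.
- Protocol section 7, item 10: an outpatient-unit visit or prescription, with no admission condition.

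**Step 2. Could another SAP field record attendance without admission?**

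- `referral` records that a referral was made, not that the person attended.
- `visits` and `date_visits` sit in the patient block and describe visits to the healthcare centre.
- The `hosp_` fields describe the hospital stay.

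None records a hospital outpatient visit by someone who was not admitted.

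**Step 3. Ceiling on Endpoint 9**

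Let *h* be the share of diagnosed people with a hospitalisation, for any reason, before the visit in question. Under the literal definition only they can have a follow-up visit, so

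reported follow-up ≤ *h* × 100%,

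however many attend. The documents do not give *h*. For illustration only:

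- *h* = 1%: at most 1%
- *h* = 5%: at most 5%
- *h* = 20%: at most 20%

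Endpoint 9 is worded as a number of patients. In that form, the ceiling is the number of diagnosed people who were admitted.

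**Step 4. Ceiling on Endpoint 10**

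Endpoint 10 draws on the electronic patient record (EPR) as well as the MBDS. The patient block of Annex 1 has `drugs`, `doses`, `tto_start` and `tto_end`, none with an admission condition. Let *e* be the share of treated people whose prescription appears in those fields (not given), and assume that admission is independent of this. Then

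share of treated people captured ≤ *e* + (1 − *e*)*h*.

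With *h* assumed to be 5%:

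- *e* = 0: 0 + 1 × 0.05 = 5%
- *e* = 50%: 0.50 + 0.50 × 0.05 = 52.5%
- *e* = 90%: 0.90 + 0.10 × 0.05 = 90.5%

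The loss for Endpoint 10 is therefore large only if *e* is also small.

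**The case against.** The strongest reply is that the intent is plain and this is a labelling slip. The objective and endpoint both refer to diagnosis, the protocol plans outpatient visits and drugs, and in Annex 1 only the visit count and visit dates carry the admission limit; the diagnosis and drug rows refer simply to follow-up visits. An analyst who knows the protocol might extract the right records. This stands as to intent, and it is why the repair needs no new data source. It does not remove the point: the limit also appears in Tables 2 and 3, and Annex 1 is the list that defines the extract.

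Three stronger readings are tempting, and the documents do not support them.

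- *Nearly every screen-detected case would be missed.* That requires a very small admission share, and the documents give none. Referral to a specialised unit is described; how many of those referred are admitted is not.
- *Endpoint 10 fails in the same way.* It does not, because its EPR drug and treatment-date fields are free of any admission condition. Protocol section 7, item 7 also separately collects drugs for the study diseases, and protocol section 8 allows for treatment as well as referral. What could be lost is treatment recorded only in hospital outpatient units for people never admitted.
- *The arms would be compared with bias because earlier detection prevents admissions.* Nothing in the documents shows that admission differs by arm.

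It is also fair to say that the stakes are modest. SAP section 2.3 lists both endpoints as exploratory, although section 2.2 labels their objectives secondary.

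**Conclusion.** The mismatch is real and confined. The SAP's hospital follow-up variables are narrower than the endpoint they serve and narrower than the protocol. Followed as written, Endpoint 9 leaves out every diagnosed person who attends the reference hospital's specialised or outpatient unit without having been admitted. The result is capped at the share admitted. The size of the shortfall depends on that unknown share; the 1% to 20% used above is an assumption, not an estimate.

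Endpoint 10 is affected only in part, to a degree set by a second unknown: how much treatment is visible in the EPR. The primary detection-rate analysis and the screening-test outcomes do not use these variables and are unaffected. This should be corrected before extraction because the correction is cheap, but it does not threaten the trial's main conclusion.

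**What to change.** 1. In SAP Annex 1, and in Tables 2 and 3 where they appear, define the follow-up visit, date, diagnosis and drug variables as relating to any specialist or outpatient visit at the reference hospital on or after the diagnosis date, whether or not the person was admitted. This brings them into line with protocol section 7, item 10. Apply the same rule to the follow-up treatment start and end dates.
2. Keep visits that follow a hospital stay as a separate descriptive field.
3. Report Endpoint 9 as a count and as a proportion of all diagnosed persons.
4. State which source holds the outpatient visits and outpatient-unit prescriptions at each site, and for Endpoint 10 how the EPR and hospital records are combined.

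The cost is a wording change in the SAP and a matching extraction request. The protocol already lists outpatient visits and drugs, so no new type of data has to be added to the plan.
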